## Background

Knee arthroscopy is a minor outpatient orthopedic procedure, used primarily to remove loose bodies, for debridement of meniscal tears, debridement and remodeling of cartilage lesions, ligament reconstruction, meniscus transplants, and arthroscopically assisted synovectomy[1].

Estimates made in the United States of America indicated that in 2006, 6.3 million orthopedic surgical procedures were performed in an outpatient context[1], of which 984,999 (95% CI: 895,999 to 1,073,215) corresponded to knee arthroscopies[1 ]. In Sweden it is estimated that a team consisting of an average of 7 surgeons (from teaching, general and local hospitals) performs 330 (110-2,600) arthroscopies annually[2].

Post-surgical pain after performing knee arthroscopies has been described in 62.5% of patients acutely (4 days after the operation), and in 76.9% of subjects chronically (1 year after surgery)[3]. In patients with moderate-severe preoperative pain (4-10 points according to the visual analogue scale (VAS)), the presence of acute and chronic pain occurs in 45.6% and 42.7%, respectively, while in those with pain between 0 -3 points, acute and chronic pain occurred in 17.2% and 6.9%, respectively[3].

Global Surgical Recovery has been investigated using the Global Surgical Recovery Index after knee arthroscopy, the evaluation tool consisted of a question “Yes, 100% recovery means that your health “You have returned to the same level you had before the surgery, what percentage of recovery do you have now?” (“if 100% recovery means your health is back to the same level as it was before the surgery, what percentage of recovery are you now?”), with 88.5% of participants responding with values  $\leq 80\%$  in a period of 4 days after surgery and 50.0% values  $\leq 80\%$  one year after surgery[3].

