### **Justification**

The prevalence of moderate-severe pain in post-knee arthroscopy patients is 71.2%. The prevalence of acute postoperative pain is 37.5% and chronic pain is 37.7%, exceeding the prevalence compared to that of other surgical procedures of different specialties.

This study will provide evidence regarding the effect of an anesthetic on postoperative pain control, as well as the effects on reducing opioid consumption and patient mobilization.

The administration of opioids is part of a common practice in pain management, however it represents a risk for patients due to their adverse effects and high risk of dependence. It is necessary to look for alternatives that reduce opioid consumption in postoperative patients, taking care of the cost-benefit for the patient as well as for health institutions.

The reduction in postoperative pain with the applied strategies that has been observed is up to 30% in the immediate postoperative (1st measurement), 20% at 8 hrs (2nd measurement) and 10% at 24% (3rd measurement).

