### *Selection criteria*

- Mental health: healthy (not taking any medication)
- Articular cartilage lesion Grade I, II or III by Outerbridge
- Elective knee surgery
- Patients with any of the following diagnoses:
- Simple menisc lesion

-Lesion of a single knee (unilateral)

*Exclusion criteria*

- Neuromotor diseases (alterations in step, strength or sensitivity)
- History of knee surgery (orthopedic)
- Instability that includes knee ligament lesions
- Addictions
- Mental diseases in medical treatment
- Hepatic diseases
- Allergy to any of the medications used in the study
- Epidural or peridural anesthesia
- Chronic pain in treatment
- Postoperative drain of knee arthroscopy
- Pregnant or lactating

*Model description*

After confirming that the patients meet the selection criteria, they will be invited to participate in the study. Upon accepting through signed informed consent, the physician in charge of randomization (physician 1) will be informed and the surgery scheduled. The day of the surgery, the physician in charge of randomization will report the maneuver to be received from the anesthesiologist (physician 2) in charge, who will prepare the dose of ropivacaine and give it to a physician blinded to the maneuver (physician 3); this physician will apply the ropivacaine intraarticular to the patient. The level of pain will be evaluated two hours after the end of surgery by a physician blinded to the maneuver the patient has received (physician 4), while the patient is in his room, and the presence of acute-moderate-severe pain (4-10 points) is evaluated by a visual analog scale (EVA) while the patient is requested to flex and extend the knee.

*Randomization:*

Randomization will be performed by number generator software OxMaR (Oxford Minimization and Randomization).

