### *Sample size*

Expecting an absolute difference, an absolute difference of 30% is expected for the presence of moderate-severe pain, considering a level of significance=5% and power=80%. Needed are 68 subjects, 34 for each arm.

Given that the evaluation of outcome is performed 2 hrs. after the application of the maneuver, and due to the low incidence of postoperative anesthetic complications, loss of information is estimated at <1%.

*Sample size and statistical analysis:* Sample size was estimated to establish a difference of 30% in considering the presence of moderate-severe pain among patients treated with different doses of ropivacaine, considering an alpha level of 0.05 and beta of 0.20. Required

were 68 patients divided into two groups of 34 each. Loss of information was expected at <1%, and 2 subjects were added to the sample size, increasing the requirement to 70 subjects in total. For statistical analysis, the statistical program SPSS version 27 will be used (IBM Armonk, New York). Contrast of the incidence of outcomes between the two groups by different doses of ropivacaine will be carried out by  $\chi^2$  or Fisher exact test, when necessary. Multivariate analyses will be performed by logistic regression analysis, considering a value of  $p < 0.05$  as significant, and double gradient differences in exposure to different variables between treatment groups were included in multivariate analysis.

In the *intention-to-treat analysis* (ITT), the main and secondary outcomes will be contrasted between the groups, considering the randomization of the different doses of ropivacaine, and in the *per-protocol analysis (PP)*, the results of the incidence of moderate-severe pain will be contrasted between groups formed by randomization; however, those that received opioids in the first 2 hours post-surgery will be excluded, in order to know the effect of the use of ropivacaine at 7.5% without the effect of a conjugate maneuver.

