#### *Variables to be evaluated*

Dependent variable	
Pain (Primary outcome)	Conceptual definition: Sensory and emotional experience associated with a present or potential injury or a described one.  Operational definition: The sensation of painful discomfort at the surgical site (Mild, moderate or severe).  Type of variable: Dichotomous qualitative.  Measuring instrument: VAS (0-10 points)  Measurement units: Mild 0-3 points, moderate-severe 4-10 points.

Opioid use	
Conceptual definition: Drug whose analgesic action is produced thanks to the interaction with the opioid receptors of the neurons of the central nervous system.
 
Operational definition: According to the VAS pain score administration of Tradol dose of 50mg IV.
 
Type of variable: Qualitative dichotomous
 
Measuring instrument: Information extracted from the patient's file.
 
Measurement units: Not use / Use.

Mobility	
Conceptual definition: Amplitude of joint oscillation within natural limits.
 
Operational definition: The active mobility performed by the patient in the postoperative period.
 
Variable type: Dichotomous qualitative.
 
Measuring instrument: Observation made by the doctor in the postoperative period after the indication of flexion and extension of the leg, elevation and descent of it actively before the doctor.
 
Measurement units: Present / absent.

Independent variable	
Ropivacaine 0.75%	
Conceptual definition: Long-lasting amide-type local anesthetic with lower lipid solubility.
 
Operational definition: IA administration to the knee of 10 ml of 0.75% ropivacaine.
 
Variable type: Dichotomous qualitative.
 
Measuring instrument: Experimental maneuver.

	Measurement units: No / Yes
Ropivacaine 0.2%	
Conceptual definition: Long-acting amide-type local anesthetic with lower lipid solubility
 
Operational definition: IA administration to the knee of 10 ml of 0.2% ropivacaine.
 
Variable type: Dichotomous qualitative.
 
Measuring instrument: Experimental maneuver.
 
Measurement units: No / Yes

Peripheral variables/covariates/Probable confounders /Probable interactors	

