Sex	
Conceptual definition: Organic condition of the individual.
 
Operational definition: Identification of the individual as Male or Female.
 
Type of variable: Dichotomous qualitative.
 
Measurement units: Male / Female.

Age	
Conceptual definition: Time lived by a person.
 
Operational definition: 18-35 years; 36 – 60 years.
 
Variable type: qualitative ordinal
 
Measurement units: 18-35; 36-60

BMI	
Conceptual definition: Mathematical reason that associates weight and height.
 
Operational definition: 1. normal weight BMI<25 vs 2. overweight BMI≥25

	
Variable type: qualitative ordinal
 
Measurement units: kg/m^2

Time of evolution	
Conceptual definition: Duration from the onset of symptoms or their detection
 
Operational definition: 1. <4 weeks and 2. >5 weeks
 
Variable type: qualitative ordinal
 
Measurement units: number of weeks

Physical activity	
Conceptual definition: Any body movement produced by skeletal muscles that requires energy expenditure
 
Operational definition: active vs sedentary
 
Variable type: dichotomous qualitative
 
Measurement units: 0-1

Etiology of surgery	
Conceptual definition: Cause of the organism before the disease
 
Operational definition: traumatic vs degenerative
 
Variable type: dichotomous qualitative
 
Measurement units: 0-1

Duration of Surgery	
Conceptual definition: Time spent performing interventions inside and outside the human body
 
Operational definition: 1. <45 min and 2. <math>\geq</math> 45 min
 
Variable type: qualitative ordinal
 
Measurement units: minutes

Type of articular cartilage injury	
Conceptual definition: Description of the different degrees of chondropathy
 
Operational definition: I: 0mm, II: < 0.5mm and III : >0.5mm
 
Variable type: qualitative ordinal
 
Measurement units: millimeters

---	--

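### The covariate rule for the logistic model is undefined and, on its words, selects on chance differences between arms, so the adjusted model cannot be fixed in advance (minor)

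*Combined protocol and SAP*

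**What the plan says.** All references are to the combined protocol and SAP.

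- **Main contrast** (Sample size, paragraph on sample size and statistical analysis): "Contrast of the incidence of outcomes between the two groups by different doses of ropivacaine will be carried out by" a chi-square test, or Fisher's exact test when necessary. This is unadjusted.
- **Adjusted model** (same paragraph): a logistic regression judged at p < 0.05, with the entry rule "double gradient differences in exposure to different variables between treatment groups were included in multivariate analysis". No statistic, threshold or reference level is given, and the term appears nowhere else. The role of the model (primary, supportive or sensitivity) is not stated.
- **Candidates** (Variables to be evaluated, under "Peripheral variables/covariates/Probable confounders /Probable interactors"): sex, age, BMI, time of evolution, physical activity, etiology, duration of surgery and type of cartilage injury.
- **Allocation** (Randomization, under Selection criteria): "Randomization will be performed by number generator software OxMaR (Oxford Minimization and Randomization"). No minimisation factor is named.
- **Pre-operative pain**: the Background cites a cohort in which acute pain, assessed 4 days after the operation, differed by pre-operative VAS: 45.6% with 4-10 points against 17.2% with 0-3 points. No section lists or schedules a pre-operative VAS. The only pain assessment scheduled in the Methods is at 2 hours.

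**The concern.** A covariate earns its place in a randomised comparison by predicting the outcome. This rule asks instead whether the arms differ. For baseline factors, randomisation makes any such difference chance. The same holds for duration of surgery and cartilage grade, which are settled before the injection, provided the surgeon does not know the allocation. The rule can therefore admit variables unrelated to pain and leave out strong predictors that happen to be balanced.

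Because the term is undefined, two analysts holding the same data could fit different models and both claim to follow the plan. What is at stake is whether the adjusted odds ratio can be reproduced, plus a little precision.

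**Working it through.** **1. The plan's own figure.** Inputs: 37.5% against 7.5% (Abstract), and "considering an alpha level of 0.05 and beta of 0.20" (Sample size). Sidedness is not stated, so two-sided is assumed. The exact power of Fisher's test, by binomial enumeration, is 79.4% at 33 per arm and 81.0% at 34. The stated 34 per arm is reproduced, and nothing below changes it.

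**2. How many covariates the data can carry.** Expected events in 70 patients: 35 × 0.375 + 35 × 0.075 = 13.125 + 2.625 = 15.75.
- Treatment plus two one-coefficient covariates: 15.75 / 3 = 5.25 events per coefficient.
- Treatment plus all eight candidates (nine coefficients, as cartilage injury has three grades): 15.75 / 10 = 1.6.

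**3. How often one unrelated binary factor enters.** Assumptions: the rule means a two-fold ratio on either level, and randomisation is simple. With X and Y the counts in the two arms, each Binomial(n, π), entry occurs if the larger count is at least twice the smaller for either level. The probabilities of all pairs that meet this are summed exactly.

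| Prevalence π | n = 34 | n = 35 |
|---|---|---|
| 20% | 22.2% | 21.4% |
| 30% | 9.8% | 9.3% |
| 40% | 3.8% | 3.5% |
| 50% | 1.8% | 1.6% |

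For seven such factors at 35 per arm, the expected number entering is 7 × 0.2135 = 1.5 at 20%, 7 × 0.0930 = 0.65 at 30%, and 7 × 0.0159 = 0.11 at 50%. The chance that at least one enters is 1 − (1 − 0.2135)^7 = 81%, 1 − (1 − 0.0930)^7 = 50%, and 1 − (1 − 0.0159)^7 = 11%.

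**4. The rule does not track the size of the imbalance (34 per arm).**
- At 20% prevalence, an imbalance of 20 percentage points or more triggers entry in 4.8% of trials. The other 22.2 − 4.8 = 17.4 points of entries are on smaller imbalances.
- At 50% prevalence, an imbalance of 20 points or more occurs in 11.4% of trials. Only 1.8 points of these trigger entry, so 11.4 − 1.8 = 9.6 are missed.
- The level counted matters. For a 30/70 factor, entry is 9.8% if the rarer level counts and 0.02% if only the commoner level does.

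**5. Effect on the result.** Simulations used 35 per arm and the planned rates, with covariates unrelated to pain.
- Odds ratio: the planned value is (0.075/0.925) / (0.375/0.625) = 0.135. The median estimate is 0.132 unadjusted. With the rule it is 0.128, 0.132 and 0.132 at 20%, 30% and 50% prevalence. The typical shift is slight.
- Power by likelihood-ratio test, prevalence 20% to 40%, pre-operative pain odds ratio 4: about 88-90% under the rule, 89-90% unadjusted, and 91-92% with pre-operative pain fixed in advance. The rule costs about 0.5 to 1.5 points, least where few covariates enter. Type I error is near nominal in all three.

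These powers exceed the 81.0% in step 1 because the test differs. Only the differences between them matter here.

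**6. Pre-operative pain.** The Background's figures give (0.456/0.544) / (0.172/0.828) = 4.04. Power at 35 per arm, unadjusted / adjusted for pre-operative pain in two groups:

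| Prevalence of VAS 4-10 (assumed) | Odds ratio 4 | Odds ratio 2 |
|---|---|---|
| 30% | 0.894 / 0.915 (+2.1 points) | 0.894 / 0.897 (+0.3) |
| 50% | 0.892 / 0.913 (+2.1) | 0.901 / 0.902 (+0.1) |
| 70% | 0.891 / 0.903 (+1.2) | 0.903 / 0.901 (−0.2) |

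The second column shows no real gain. The cohort figures are only indicative, since they concern 4 days, not 2 hours. The Background's overall acute rate of 62.5% also lies outside 17.2% to 45.6%, while the 37.5% in the Justification lies inside.

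**The case against.** **The sizes rest on a guess.** The two-fold reading is not in the text, the prevalences are not given, and the past tense of the sentence suggests loose translation. This stands, so the figures in steps 3 to 5 illustrate one possible rule. It does not rescue the plan: the sentence names differences between treatment groups as the criterion, and that is the wrong criterion at any threshold. If OxMaR minimises on a factor, its entry rate would be lower than shown.

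**There is almost no harm.** Largely true, and the reason for the low severity. A reader might infer that selecting on imbalance inflates the type I error or undermines the main result. Neither is supported: simulated type I error is near nominal, and the main contrast uses no covariates.

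**Leaving out pre-operative pain is not an error.** Agreed. Omitting a baseline covariate from an adjusted model in a randomised trial is a choice. The link at 2 hours is assumed, and the selection criteria (simple meniscal lesion, one knee, no previous knee surgery, no chronic pain in treatment) already narrow baseline variation. It is offered only as an option. A reader might also infer that pre-operative pain will not be recorded. The documents show only that no section lists or schedules it; the data forms are not included.

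**The model's role and the list.** It is tempting to call the model supplementary and the covariate list closed. The plan says neither.

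**Conclusion.** The point holds and is minor. The entry rule is undefined and, on its words, selects covariates by chance differences between arms without regard to prognosis. The adjusted model cannot be fixed in advance or reproduced from the plan. Under the two-fold reading, simple randomisation, 35 per arm and unrelated covariates at 20% to 40% prevalence, the cost is about 0.5 to 1.5 points of power against the unadjusted analysis. The sample size and the unadjusted chi-square or Fisher contrast are unaffected. The unstated role of the logistic model is a related gap, best closed in the same edit.

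**What to change.** 1. Delete the rule based on differences between arms.
2. Before unblinding, name the adjusted model as treatment plus at most two covariates, chosen on prognostic grounds.
3. If OxMaR minimises on any factors, name them and give them priority for the two places. If there are more than two, include them all and state the lower events per coefficient. Three one-coefficient factors, for example, give 15.75 / 4 = 3.9.
4. State that the adjusted model supports the unadjusted intention-to-treat contrast.
5. Optional: add one pre-operative VAS mark to the form and enter it as a continuous score in one of the covariate places. The gain is about 1 to 2 power points over unadjusted if the odds ratio at 2 hours is about 4, and none if it is about 2. Those figures used a two-group split; the continuous form was not simulated.

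**Cost.** Items 1 to 4 need a few sentences in the analysis section and no new data, if the covariates come from the existing list. Item 5 adds one form item.

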## **The American British Cowdray Medical Center**

**Date: March 26, 2020**

**NCT05807945**

### **Comparison of Intra-articular 0.2% Ropivacaine vs 0.75% Ropivacaine in Postoperative Knee Arthroscopy**

#### **Abstract:**

All patients with acute lesions assistant to the orthopedic and trauma center of the ABC medical center will be invited to participate in the study. Those that meet the inclusion criteria and later sign an informed consent will be randomized to receive 10 ml of a solution with ropivacaine at 0.75% and 0.2% intraarticular for the first 5 minutes after the end of surgery (closing of surgical wounds). Both the patient, the physician who applies it and the evaluator of outcomes remain blinded to the dose of ropivacaine the patient receives.

Two hours after the end of the surgery, while the patient is in his room, the presence of pain will be evaluated by a visual analog scale (EVA), while the patient is asked to flex and extend his knee. The result will be quantified continuously, to later categorize the pain in none to slight pain (0-3 points) and moderate-severe pain (4-10 points). All the information will be recorded on established forms in the clinical file (general data), that includes the variables of interest for the study, and is reported by the physicians after standardization of all those encharged with collecting information to comply with the conceptual and operative

operationalization of the variables described in the research protocol. In addition to the evaluation of pain, the administration of opiodes to patients for necessary reasons (presence of pain) by the physicians in charge is recorded.

It is hoped that, in patients with knee arthroscopy for acute lesion, there is a difference in the frequency of moderate-severe pain of 30% in the post-operative (frequency of 37.5% in patients with ropivacaine at 2% and frequency of 7.5% in patients with ropivacaine at 7.5%).

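### The primary outcome has no rule for opioids given for pain before the 2-hour reading, so rescue may dilute, by an unknown amount, the ropivacaine difference in the intention-to-treat analysis

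*Combined protocol and SAP*

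**What the plan says.** - **Outcome and timing.** The Abstract states: "Two hours after the end of the surgery, while the patient is in his room, the presence of pain will be evaluated". The Variables table makes this a two-level outcome, 0-3 against 4-10 points. Opioid use is not part of the definition.
- **Opioids.** The Abstract says that opioids given because of pain are recorded. The Variables table makes opioid use a separate yes/no outcome, defined as: "According to the VAS pain score administration of Tradol dose of 50mg IV".
- **ITT analysis** (Sample size section): "the main and secondary outcomes will be contrasted between the groups, considering the randomization of the different doses of ropivacaine". It says nothing on opioids given before the 2-hour reading.
- **Per-protocol analysis** (same section): "those that received opioids in the first 2 hours post-surgery will be excluded". The stated reason is to see the effect of ropivacaine free of an accompanying treatment.
- **Objectives.** The general objective is the analgesic effect of the intra-articular injection in the immediate postoperative period. Opioid consumption is a specific objective.

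**The concern.** The plan foresees opioids before the 2-hour reading and says they are given for pain. A patient whose pain ropivacaine did not control, who receives an opioid and then scores 2 at 2 hours, is classified with those who never needed help. If the trial's hypothesis is true, such patients are more frequent in the 0.2% arm. Its observed rate of moderate-severe pain then falls by more percentage points than that of the 0.75% arm, and the absolute difference shrinks.

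At stake is what the ITT result answers. It describes pain at 2 hours under ropivacaine plus whatever rescue followed. The Sample size section shows that the sponsor also wants the effect without the opioid. Its only means to that end is an exclusion based on an event after randomisation that pain itself causes.

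**Working it through.** **Inputs.** The Sample size section gives the target, "an absolute difference of 30% is expected for the presence of moderate-severe pain", "considering an alpha level of 0.05 and beta of 0.20", 34 per arm, and 70 in total after two are added (35 per arm). The Abstract gives the planning rates: "frequency of 37.5% in patients with ropivacaine at 2% and frequency of 7.5% in patients with ropivacaine at 7.5" (per cent). I attach 37.5% to the lower concentration and 7.5% to the higher. The concentrations in that sentence differ from those in the title and the Maneuver section and must be reconciled. The test is chi-squared, or Fisher where needed. A two-sided test is assumed, since the plan does not say.

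**Step 1: the plan's own figure.** Exact power of the two-sided Fisher test at 37.5% against 7.5% is 79.4% with 33 per arm and 81.0% with 34. So 34 per arm is reproduced. At 35 per arm, power is 82.6% (Fisher) or 88.6% (chi-squared without continuity correction).

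**Step 2: a model for rescue.** Let m be the share of patients with moderate-severe pain who receive an opioid before 2 hours and then score 0-3. The documents give no value for m, so a range is shown. Assume that 37.5% and 7.5% are rates without rescue. Then:

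observed rate = planned rate × (1 − m)

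For m = 25%: 37.5% × 0.75 = 28.1%, and 7.5% × 0.75 = 5.6%. The difference is 22.5 points.

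| m (both arms) | Observed rates | Difference | Fisher power | Chi-squared power |
|---|---|---|---|---|
| 0 | 37.5% vs 7.5% | 30 points | 82.6% | 88.6% |
| 10% | 33.75% vs 6.75% | 27 points | 76.3% | 84.2% |
| 25% | 28.1% vs 5.6% | 22.5 points | 63.7% | 75.8% |
| 50% | 18.75% vs 3.75% | 15 points | 34.4% | 56.8% |

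All powers are exact, at 35 per arm. If the plan's choice between tests means Fisher when an expected count is below 5, power is about 88%, 83%, 71% and 38% down the table. If rescue masks pain only in the 0.2% arm, Fisher power is 72%, 52% and 17% at m = 10%, 25% and 50%.

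**Step 3: does the per-protocol exclusion restore the difference?** It removes the rescued patients, a share (planned rate × m) of each arm:

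per-protocol rate = planned rate × (1 − m) / (1 − planned rate × m)

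For m = 25%: 0.28125 / 0.90625 = 31.0%, and 0.05625 / 0.98125 = 5.7%. The difference is 25.3 points. At m = 10% it is 28.3 and at m = 50% it is 19.2. The exclusion never returns 30 points, because it drops uncontrolled pain. At m = 25% it drops 35 × 0.375 × 0.25 = 3.3 patients from the 0.2% arm against 35 × 0.075 × 0.25 = 0.7 from the other.

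**Step 4: count rescue for pain as an event.** The rate is planned rate × (1 − m) + planned rate × m = planned rate. The contrast returns to 37.5% against 7.5%, with 82.6% (Fisher) or 88.6% (chi-squared) power at 35 per arm, and no patients need be added. This assumes that every rescued patient would otherwise have scored 4-10 at 2 hours.

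**The case against.** **The ITT contrast is not wrong.** Pain at 2 hours by randomised arm, whatever rescue was given, is a valid treatment-policy comparison. The general objective asks for an analgesic effect and does not specify one without rescue. This stands: the point concerns which question the analysis answers, not an invalid test. It remains a gap because the plan does not say which effect it targets, while its per-protocol rationale asks for the effect without opioids.

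**A reader might infer that a null result could not be interpreted.** The documents do not support that. Opioid use is also compared by randomised arm, so a null VAS result with more opioid use in the 0.2% arm would be visible. That would inform the reading of the primary outcome but would not correct it.

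**A reader might infer that a VAS score is on file before every opioid dose.** The Variables table links the opioid to a VAS score but gives no time, assessor or threshold. The score could be the 2-hour reading itself, with the opioid given afterwards.

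**The size is uncertain.** The Justification section gives 37.5% as the prevalence of acute postoperative pain and describes opioids as common practice. The planning rate may therefore already include usual rescue, and the loss against planned power would then be smaller. Fisher power alone also overstates the loss. With the test chosen by expected count, power at m = 10% is still about 83%, above the planned 80%. In the equal-m model the risk ratio stays at 5.0, so only the absolute difference shrinks. All of this stands.

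**Conclusion.** The concern holds as a possible dilution of unknown size. The documents establish that the outcome is classified on the 2-hour VAS alone, that opioids for pain before that reading are foreseen, and that neither the per-protocol exclusion nor the separate opioid comparison corrects the classification. The direction, towards a smaller absolute difference, rests on the trial's own hypothesis that the 0.2% arm has more pain and hence more rescue.

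The size rests on m, which the documents do not give, and on the planning rates being free of rescue, which they do not state. The figures above are illustrations: little is lost at m = 10% and a great deal at m = 50%. A reader might go further and infer that rescue hides the drug's effect. Without a rescue rate, the documents support only that it may dilute it. The matter should be settled in the plan before unblinding.

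**What to change.** In the Sample size section, pre-specify an analysis of all randomised patients by arm in which the event is VAS 4-10 at 2 hours or an opioid given for pain in the first 2 hours. Opioid use is already recorded; its time and reason must be clear enough to apply the rule. Where a VAS taken before the opioid is available, record it and, as a refinement, count the patient as an event through rescue only if that score is 4-10.

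Use this analysis in place of the per-protocol exclusion to address the effect without rescue. Report it beside the plain 2-hour VAS result by ITT, and state before unblinding which of the two is primary.

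Costs:
- The endpoint is slightly more complex.
- It depends on opioid times or scores recorded by ward staff, not only on the single blinded evaluator.
- Some patients whose pain would have settled by 2 hours count as events, so event rates may differ from those behind the sample size.

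Rescue practice itself is unchanged.
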